Title Page

A Comparison of Two Different Anesthetic Application (Sedation / Analgesia & LMA) on Anxiety Level and Patient Satisfaction in Patients with in Vitro Fertilization: Prospective Randomized Clinical Trial

***[name]**, Asst. [name] of Anesthesiology and Reanimation, Inonu University Faculty of Medicine, Malatya, Turkey.

[name], Asst. [name] of Anesthesiology and Reanimation, Inonu University Faculty of Medicine, Malatya, Turkey.

[name], [name]. Division of Reproductive Endocrinology, Department of Obstetrics and Gynecology, Inonu University Faculty of Medicine, Malatya, Turkey.

[name]. Asst [name] of Reproductive Endocrinology, Department of Obstetrics and Gynecology, Inonu University Faculty of Medicine, Malatya, Turkey.

Address all correspondence to:

[name], Asst. [name] of Anesthesiology and Reanimation, Inonu University Medical Faculty, Malatya, Turkey

Mail: [contact]

[contact]

[contact]

A short title: Anesthesia Management of in Vitro Fertilization

Conflict of Interest:

The authors declare that they have no conflict of interest.

Funding Information:

None

Study Protocol

This trial was approved by the Local Ethic Committee of Inonu University (Protocol no: 2018/56, Approval Date: 18.04.2018). We conducted a prospective, randomized controlled clinical trial with 140 female patients undergoing in vitro fertilization (IVF) at an university hospital.

Patients with American Society of Anesthesiology (ASA) scores of I-II and who were aged 18–55 years old will be included in our study. Patients will be interviewed before surgery to obtain informed consent. Patients with ASA III-IV, under 18 years of age, over 55 years of age, uncontrolled diabetes mellitus, cardiovascular, pulmonary disease, cerebrovascular events, patients with an allergy to anesthetic drugs pregnant were excluded. Patients who refused informed consent will be also excluded.

All of the patients one day before surgery; hemoglobin, hematocrit, prothrombin time, active partial thromboplastin time, aspartate aminotransferase, alanine aminotransferase will be evaluated. Electrocardiography and preoperative anesthetic evaluations will be performed. The patients who will agree to participate in the study will fill the demographic data form and STAI TX-1 (State Anxiety Scale Scale) form 2 hours before the procedure. Standard monitoring procedures will be used, including heart rate (HR), noninvasive blood pressure (NIBP), electrocardiogram (ECG), and peripheral oxygen saturation (SpO₂).

Age, gender, height, weight, body mass index (BMI), ASA scores, laboratory values, duration of anesthesia, duration of the procedure, concomitant diseases, preoperative symptoms, anesthetic drugs and doses used, causes and duration of infertility, anesthesia and complications of surgery will be recorded. HR (heart rate), SAB (systolic arterial pressure), DAB (diastolic arterial pressure), MAP (mean arterial pressure), DSS (respiratory rate), peripheral oxygen saturation (SpO₂) values will be recorded at preoperative, peroperative and postoperative

periods. Patients, who will not experience complications during the procedure, will be transferred to the post-anesthesia care unit (PACU) after the procedure. VAS score (Visuel Analog Scale) and RAMSEY sedation score will be recorded for the patients followed up in the PACU. Patients will be transferred to the service when they achieved a score of 9 or higher on the Modified Aldrete score (range 0 –12; scores of 9 and above indicate that the patient can be discharged from the PACU). In all patients, postoperative analgesia will be achieved IV analgesic medication using appropriate doses of paracetamol (1 gr, IV). Patients will complete the QoR-40 questionnaire, which is a Patient Satisfaction Survey, 24 hours after discharge.

Randomization was performed with the MedCalc for Windows (medcalc.com.tr.), version 16 statistical software. 140 patients will be randomly allocated to two study groups: Sedation Analgesia group (Group S, $n = 70$) and Maryngeal Mask Airway, LMA (Group L, $n = 70$). Midazolam $0.05 - 0.1 \text{ mg} \cdot \text{kg}^{-1}$ IV will be performed for premedication before the procedure in both groups. No inhalation anesthetics will be used in groups. In both groups, Anesthesia will be induced and maintained with propofol $1-2 \text{ mg} \cdot \text{kg}^{-1}$ IV, remifentanil $0.05 - 0.1 \text{ mcg kg}^{-1}$ IV or fentanyl $1-2 \text{ mcg kg}^{-1}$ IV.

Statistical Analysis:

Data will be analyzed using the Statistical Package for the Social Sciences program (SPSS 22.0, IBM). As some pre and anesthetic characteristics of patients will be distributed abnormally nonparametric statistics will be used. Quantitative data are presented as mean or standard deviation and categorical data are shown as numbers or percentages. Continuous variables will be compared between the groups using Mann-Whitney U-test. Categorical variables will be summarized using frequencies and percentages (%) and compared between the groups using Chi-Squared Test. The results will be evaluated at a 95% confidence interval at a significance level of $p<0.05$.

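### QoR-40 is compared by an unadjusted test although a baseline anxiety score is already collected; the comparison is valid but gives up precision at almost no saving

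*Combined protocol and SAP*

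**What the plan says.** The title announces a comparison of two anesthetic techniques "on Anxiety Level and Patient Satisfaction in Patients with in Vitro Fertilization". The Study Protocol section mentions QoR-40 once: "Patients will complete the QoR-40 questionnaire, which is a Patient Satisfaction Survey, 24 hours after discharge". No other measure of satisfaction is named.

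The same section provides a questionnaire contact before the procedure, where patients "will fill the demographic data form and STAI TX-1 (State Anxiety Scale Scale) form 2 hours before the procedure". QoR-40 is not among those forms.

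Under Statistical Analysis, "Continuous variables will be compared between the groups using Mann-Whitney U-test". No covariate is named for any outcome, so the baseline STAI score has no part in the QoR-40 comparison. The randomisation paragraph states that "140 patients will be randomly allocated to two study groups", 70 in each. The documents give no sample-size derivation, target difference or power.

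**The concern.** A patient's recovery or satisfaction score a day after discharge may partly reflect how she felt beforehand. The protocol itself records features that could matter, such as the infertility history, other illnesses and symptoms before the procedure. With a single post-discharge score and an unadjusted test, two things follow:

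- All of the variation between patients that a baseline score could have explained stays in the error term, so the trial is less able to detect a difference of a given size.
- If the two groups of 70 differ by chance at baseline, the part of that difference that carries through to QoR-40 stays in the result. Imbalance on STAI could be seen, since continuous variables are compared between groups, but the plan has no means of correcting QoR-40 for it. Imbalance on a pre-procedure QoR-40 could not even be seen.

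At stake is the efficiency of the comparison on one of the two title outcomes. With no stated target difference or power, there is no documented margin to show that the precision can be spared.

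**Working it through.** **Inputs from the documents.** N = 140, with 70 per arm (Study Protocol, randomisation paragraph). Significance level 0.05 (Statistical Analysis); sidedness is not given, so two-sided is assumed. There is no power figure to reproduce.

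**Assumptions, none of them in the documents.** A true difference of 0.4 SD on QoR-40; a correlation r between the baseline score and QoR-40 of 0.1 to 0.5; all 140 patients analysed; approximately normal scores. The lower correlations are meant for STAI, and 0.5 for a baseline made of QoR-40 items.

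**Formulas.**

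1. Share of variance left after adjustment: 1 − r².
2. Number of unadjusted patients giving the same precision: 140 / (1 − r²).
3. Power: Φ(0.4 / √(1 − r²) × √(70/2) − 1.96).
4. Difference detectable with 80% power: (1.960 + 0.842) × √(2/70) × √(1 − r²).

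Unadjusted (r = 0), the power is Φ(0.4 × 5.916 − 1.96) = Φ(0.406) = 65.8%. At r = 0.3 it is Φ(0.4 / 0.954 × 5.916 − 1.96) = Φ(0.521) = 69.9%.

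| r | Variance left | Equivalent N | Power at 0.4 SD | Detectable at 80% power |
|---|---|---|---|---|
| 0 | 100% | 140 | 65.8% | 0.474 SD |
| 0.1 | 99% | 141 | 66.2% | 0.471 SD |
| 0.2 | 96% | 146 | 67.6% | 0.464 SD |
| 0.3 | 91% | 154 | 69.9% | 0.452 SD |
| 0.5 | 75% | 187 | 78.0% | 0.410 SD |

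**Chance imbalance.** The standard error of a baseline difference between arms is √(2/70) = 0.169 SD, so its 95% range is ±1.96 × 0.169 = ±0.33 SD. The part that passes into the unadjusted QoR-40 difference is r × 0.33: about ±0.07 SD at r = 0.2, ±0.10 at 0.3 and ±0.17 at 0.5. The last is about 41% of a 0.4 SD effect (0.166 / 0.4). This is the same loss of precision seen another way, not a further loss.

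**Choice of test.** The table uses normal theory. Under normality the Mann-Whitney test has relative efficiency 3/π = 0.955, so its detectable difference is 0.474 / √0.955 = 0.485 SD. The first row therefore slightly flatters the planned test if scores are normal. If they are skewed, a rank method may do better, which is why a rank-based form of adjustment should be available.

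**Change scores.** If a baseline QoR-40 were collected, a simple change score would have variance 2(1 − r) relative to the post-procedure score: 1.4 at r = 0.3 and 1.0 at r = 0.5. It would be worse than no baseline below r = 0.5. The baseline must enter as a covariate.

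**The case against.** The strongest reply is that nothing here is an error. A post-only comparison of randomised groups is a legitimate design with a correct type I error. A reader might infer that differences in the patients' prior state confound the QoR-40 result. The documents do not support that: allocation is random, so such differences are balanced on average and the unadjusted test already allows for their chance variation. This part of the objection stands in full.

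Second, every figure for the gain rests on assumed values. Nothing in the documents shows that STAI before the procedure predicts QoR-40 a day after discharge. Eligibility (ASA I–II, with several major diseases excluded) narrows the spread between patients. At r = 0.1 or 0.2 the gain is under two points of power. This also stands, and it limits how strongly the change can be pressed. It does not remove the case for it, because the STAI score is already in hand and one covariate costs one of 138 residual degrees of freedom.

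Third, the protocol describes QoR-40 as a satisfaction survey, and satisfaction with an anesthetic not yet given has no baseline. This restricts a baseline form to items that make sense beforehand, and makes r = 0.5 less certain. It does not touch adjustment for STAI.

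Fourth, the plan deliberately chose nonparametric tests, and Mann-Whitney takes no covariate. That is correct, so the test for this outcome has to be replaced; an added sentence about adjustment would not do.

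A reader might also take QoR-40 to be the only patient-reported measure after the procedure. That goes too far: a VAS score is recorded in the recovery unit, with no clock time and no statement of what it rates. The point needs only that QoR-40 is the sole named measure of satisfaction.

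**Conclusion.** The point holds as a loss of precision. The plan compares a title outcome without using a baseline score it already collects, and leaves chance imbalance uncorrected. For an assumed 0.4 SD difference at 70 per arm and two-sided 0.05, adjustment would raise power from 65.8% to 67.6% (r = 0.2), 69.9% (r = 0.3) or 78.0% (r = 0.5). STAI alone may sit at the low end, where the gain is small; the larger figure would need a baseline of QoR-40 items and a correlation of 0.5.

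The figures do not show that the trial is underpowered, since the documents state no target difference. The change is worth making because it costs almost nothing, not because the planned comparison is invalid.

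**What to change.** 1. In Statistical Analysis, pre-specify that QoR-40 is compared between arms by ANCOVA adjusting for the baseline STAI score, or by a rank-based ANCOVA such as Quade's method if the scores are skewed. State the rule for choosing between them in advance. This replaces the unadjusted Mann-Whitney test for this outcome only. The document mixes past and future tense; if data collection has begun, this step is still open provided it is fixed before QoR-40 is examined by group.
2. Confirm in the Study Protocol that STAI is completed before the group is disclosed and before midazolam premedication. The documents do not say when disclosure occurs, and place premedication only at some time ahead of the procedure. A covariate affected by either would be a poor baseline.
3. Where feasible, give the QoR-40 items that can be answered beforehand at the same contact, under the same two conditions, and add that score to the model as a covariate, not as a change score.

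Steps 1 and 2 need no new data and make the analysis slightly more complex to run and report. Step 3 costs a few minutes of patient time at an existing contact.

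### Anxiety is measured only before the procedure, so the plan cannot show an effect of the delivered anaesthetic technique on it

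*Combined protocol and SAP*

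**What the plan says.** The title announces a comparison of two anaesthetic techniques "on Anxiety Level and Patient Satisfaction in Patients with in Vitro Fertilization". The documents list no separate objectives or endpoints, so the title is the only statement of what is to be compared.

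Under Study Protocol, patients who agree to take part fill in a demographic form and the "STAI TX-1 (State Anxiety Scale Scale) form 2 hours before the procedure". The STAI is not mentioned again. After the procedure the plan describes:

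- PACU scores: "VAS score (Visuel Analog Scale) and RAMSEY sedation score will be recorded for the patients followed up in the PACU".
- A later questionnaire: "Patients will complete the QoR-40 questionnaire, which is a Patient Satisfaction Survey, 24 hours after discharge".

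On allocation, "140 patients will be randomly allocated to two study groups". The text does not say when patients are randomised, when they learn their group, or whether they are blinded.

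Statistical Analysis does not name the STAI. Its general rule is: "Continuous variables will be compared between the groups using Mann-Whitney U-test".

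**The concern.** An outcome can show an effect of a treatment only if it is measured after that treatment is given. Here the single anxiety score precedes both techniques, yet the general rule for continuous variables would compare it between groups as though it were an outcome.

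What such a comparison means depends on a fact the plan omits:

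- **Allocation unknown at the form.** A significant difference would be a baseline imbalance, and a null result would say nothing about the techniques.
- **Allocation known at the form.** A difference would be evidence about anticipation of the assigned technique. A conclusion that one technique lowers anxiety would still be unsupported.

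A reader could not tell which case applies. One of the two questions in the title would go unanswered for the technique as delivered, and neither more patients nor a different test on the same data would change that.

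**Working it through.** **1. What is measured, and when.** The plan states no figure on this point, so the check starts from the assessments under Study Protocol.

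| Assessment | Time | What the plan says it measures |
|---|---|---|
| STAI TX-1 | 2 hours before | State anxiety |
| Vital signs | Before, during, after | Circulation and respiration |
| VAS | PACU | Not stated |
| Ramsay score | PACU | Sedation |
| Modified Aldrete | PACU | Readiness to leave the PACU |
| QoR-40 | 24 hours after discharge | Satisfaction |

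Only the first row is called an anxiety measure. Statistical Analysis offers Mann-Whitney and chi-squared tests between groups. It has no change score, baseline adjustment or repeated-measures analysis that would imply a second STAI.

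**2. The planned comparison if allocation is unknown at the form.** Inputs from the documents: 70 per group, Mann-Whitney, significance level 0.05. Assumptions: two-sided test, normal scores, pre/post correlation r = 0.5, and the true effects shown. The pre-procedure score is independent of group, so the rejection rate must equal 0.05 whatever happens later. Simulation (20,000 trials per setting) sets this beside a score taken afterwards:

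| True post-procedure effect | Pre-procedure STAI, Mann-Whitney | Post-procedure STAI, Mann-Whitney | Post-procedure STAI, ANCOVA |
|---|---|---|---|
| 0.25 SD | 5.0% | 30.0% | 39.5% |
| 0.5 SD | 5.0% | 81.7% | 92.5% |
| 1.0 SD | 5.0% | 100% | 100% |

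**3. The planned comparison if allocation is known at the form.** With an assumed anticipation difference of 0.1, 0.2 or 0.3 SD, the test rejects in 8.8%, 21.1% or 40.4% of trials (40,000 simulated trials each). That is legitimate power for a question about anticipation. It becomes an error only if the result is credited to the technique as delivered.

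**4. What a second STAI could detect.** Assumptions: 80% power and two-sided 0.05.

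- Normal approximation at 70 per group: (1.960 + 0.842) × √(2/70) = 2.802 × 0.169 = 0.47 SD. The exact noncentral t calculation gives 0.477 SD.
- Mann-Whitney under normality: divide by √(3/π) = 0.977, so 0.477 / 0.977 = 0.488 SD.
- ANCOVA with r = 0.5: multiply the t-test figure by √(1 − 0.5²) = 0.866, so 0.477 × 0.866 = 0.413 SD.

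| Patients per group with a second form | t-test | Mann-Whitney | ANCOVA, r = 0.5 |
|---|---|---|---|
| 70 | 0.477 | 0.488 | 0.413 |
| 50 | 0.566 | 0.579 | 0.490 |
| 35 | 0.679 | 0.695 | 0.588 |

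At 70 per group, ANCOVA gives 0.455 SD for r = 0.3 and 0.341 SD for r = 0.7. The rows for 50 and 35 are examples, because the documents do not say how many patients remain to be treated.

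**The case against.** The strongest counter-reading is that anticipatory anxiety is the intended question. Consent and the preoperative anaesthetic evaluation come before the procedure, so patients may know their group when they complete the form. The between-group comparison would then be valid, and the title does not itself say that the technique must have been delivered. This stands as a possible reading, but the plan neither states that aim nor says when allocation is disclosed. Even on this reading, the data say nothing about the technique once given.

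Other points have some force:

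- The text gives one time point but never says the form is used only once, and the protocol is very short. A second STAI may be undescribed rather than absent. The investigators should confirm this, but the plan as written contains none.
- The PACU VAS might be meant for anxiety. Nothing says so, and it is recorded only for patients followed there.
- A pre-procedure difference need not be pure chance. No allocation concealment is described, so selection at allocation could also produce one. That would still not be an effect of the technique.
- The 5% figure is simply the significance level. The simulation illustrates the point, and the argument does not depend on it.
- The trial may be over: "Randomization was performed with the MedCalc for Windows" is in the past tense while most of the text is in the future. This changes the remedy but leaves the defect in place.

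**Conclusion.** The concern holds. As written, the plan cannot show an effect of the delivered technique on anxiety, one of the two outcomes in its title. That conclusion rests on the timing alone and needs no assumed number.

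The size given above depends on assumptions: normal scores, a two-sided test, 80% power, a correlation of 0.5, and the listed effects and patient numbers. None of these except the 70 per group and the 0.05 level comes from the documents. The loss is complete where allocation is unknown at the form: power for the delivered technique equals the 5% error rate. Where allocation is known, the comparison answers a different question that the plan does not state. The QoR-40 satisfaction outcome is unaffected.

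This must be fixed before any anxiety result is interpreted.

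**What to change.** The investigators should first state whether enrolment is open, whether any second STAI is already being collected, and whether outcome data have been examined.

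**If patients remain to be treated:**

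1. Add a second STAI TX-1 at one fixed time after the end of the procedure, the same in both groups. Two hours would mirror the first form, but no length of stay is given, so feasibility must be confirmed. Time it from the end of the procedure, not from PACU exit or discharge.
2. Collect it from every randomised patient. The plan says "Patients, who will not experience complications during the procedure, will be transferred to the post-anesthesia care unit (PACU) after the procedure", so a form tied to the PACU could miss patients with complications. Report missing second forms per group, with reasons.
3. Compare the second STAI between groups by ANCOVA, or rank-based ANCOVA if skewed, with the first score as covariate. Report the adjusted difference with its 95% CI. The planned Mann-Whitney test on the second score would also cure the defect; ANCOVA adds precision.
4. State whether the first form precedes disclosure of allocation, and for remaining patients complete it before disclosure so that it is a true baseline. Where it came after disclosure, also report the unadjusted comparison, because the covariate may itself reflect allocation.

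The cost is one repeat of a self-completed form already in use, an amendment to the assessment schedule and Statistical Analysis, and ethics committee approval of that amendment. No extra patients or procedures are needed. Patients already treated have no post-procedure score, so the detectable difference grows as fewer remain. With 35 per group, Mann-Whitney power for 0.488 SD falls from 80% to 50%.

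**If enrolment is closed:** keep reporting the STAI but label it pre-procedure anxiety, state when allocation was disclosed, and reword the title and conclusions so that they claim no effect of the delivered technique on anxiety. This costs only wording.

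### Patient satisfaction, one of the two outcomes in the title, is measured only by QoR-40, so a quality-of-recovery difference would be reported as a satisfaction difference.

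*Combined protocol and SAP*

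**What the plan says.** The Title Page describes a randomized comparison of two anesthetic approaches "on Anxiety Level and Patient Satisfaction in Patients with in Vitro Fertilization". There is no objectives section and no named primary endpoint, so the title is the only statement of what the trial sets out to compare.

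The Study Protocol ties satisfaction to one instrument: "Patients will complete the QoR-40 questionnaire, which is a Patient Satisfaction Survey, 24 hours after discharge". It does not expand the abbreviation, list the items or subscales, or say why the score may stand for satisfaction.

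The Statistical Analysis section names neither QoR-40 nor satisfaction. The score therefore falls under the general rule: "Continuous variables will be compared between the groups using Mann-Whitney U-test".

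**The concern.** How well a patient has recovered and how satisfied she is with her anesthetic are different questions. Two techniques could differ on one and not on the other, or differ on both to different degrees. The arms here are sedation with analgesia and a laryngeal mask, so satisfaction would naturally mean the patient's own judgement of the technique she received.

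Under the plan, the between-group p-value for QoR-40 becomes the satisfaction result, because the protocol gives the score that label and offers nothing else. A difference in recovery would be published as a difference in satisfaction. A null result on recovery would be published as no difference in satisfaction. In neither case would the data contain a direct answer from the patient to check the statement against.

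**Working it through.** The question is what the instrument measures, and the plan has no figure to reproduce on that. The check was to go through every assessment in the protocol and ask whether it could serve as a measure of satisfaction.

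| Assessment | When | Described as satisfaction? |
|---|---|---|
| STAI TX-1 | Before the procedure: "STAI TX-1 (State Anxiety Scale Scale) form 2 hours before the procedure" | No; a state anxiety form, completed before either technique is used |
| Demographic form, laboratory tests, ECG, preoperative evaluation | Before the procedure | No |
| Heart rate, blood pressures, respiratory rate, oxygen saturation | Before, during and after | No |
| Durations, drugs and doses, infertility history, complications | Recorded for each patient | No |
| VAS and Ramsay score | Recovery unit: "VAS score (Visuel Analog Scale) and RAMSEY sedation score will be recorded for the patients followed up in the PACU" | No; the Ramsay score is for sedation, and the subject of the VAS is not stated |
| Modified Aldrete score | Recovery unit | No; it decides transfer out of the unit |
| QoR-40 | A day after discharge | Yes, by label only |

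The reasoning then runs as follows.

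1. The title requires a satisfaction result.
2. QoR-40 is the only assessment the protocol describes as measuring satisfaction.
3. Assumption: QoR has its ordinary meaning, quality of recovery. The protocol does not spell this out.
4. Under that assumption, the only satisfaction measure is a recovery score carrying a satisfaction label.
5. The Statistical Analysis section neither corrects the label nor defines a separate satisfaction endpoint, so the label passes unchanged into the reported result.

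No power calculation is given. The plan states 140 patients, 70 per group, without an effect size, standard deviation or target power. It also says nothing about how closely recovery and satisfaction move together. Any figure for lost power would come entirely from assumed inputs.

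**The case against.** The strongest reply is that the documents say only one thing about QoR-40, namely that it is a satisfaction survey, and that calling it a recovery score means expanding an abbreviation the protocol leaves alone. This stands in part. The meaning of QoR is therefore stated here as an assumption, and nothing is claimed about the questionnaire's items or domains. What remains is that the plan equates a named score with satisfaction, gives no justification and has no direct item.

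A second reply is that patients who recover well tend to be satisfied, so the score is informative. That is probably true, and it limits the point to a wrong label and a missing direct measure.

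A third is that the VAS might be a satisfaction scale. The protocol does not say what it rates. It lists it beside a sedation score in the recovery unit and attaches the word satisfaction only to QoR-40.

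A reader might also infer more than the documents support:

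- **That QoR-40 tells us nothing about satisfaction.** Nothing in the documents shows this, and some correlation is likely.
- **That it would miss particular experiences of one technique.** Without the item list, this cannot be checked.
- **That the timing is itself a fault.** The text leaves open which discharge is meant. The only one it describes is from the recovery unit, where "scores of 9 and above indicate that the patient can be discharged from the PACU". The point here does not depend on timing.
- **That the trial loses a stated amount of power.** This would need an assumed effect, an assumed correlation and a direct rating free of measurement error. A correlation between patients also does not determine how a treatment effect passes from one outcome to the other.

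**Conclusion.** The point holds as a matter of labelling and of a missing direct measure. Satisfaction is one of the two titled outcomes. Its only instrument is, on the ordinary reading of its name, a quality-of-recovery score, and a result on that score would be reported as a result on satisfaction.

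The conclusion rests on two things. One is the assumption about what QoR means. The other is reading the title as the statement of outcomes, since the documents contain no other. Confidence is moderate because of the first.

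The consequence is for what may be concluded. QoR-40 can support a statement about recovery, but not, by itself, the titled statement about satisfaction. The size of any resulting error cannot be estimated from the documents. The change should be made; the QoR-40 comparison is not invalid without it.

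**What to change.** 1. In the Study Protocol, delete the clause that calls QoR-40 a satisfaction survey, and report the score as quality of recovery.
2. At the same contact, add one direct 5-point rating of satisfaction with the anesthetic. Name that single item as the satisfaction outcome. Any question on whether the patient would choose the same technique again is secondary.
3. In the Statistical Analysis section, name the item and state that it is compared between groups with the Mann-Whitney test. This needs saying because that section assigns Mann-Whitney to continuous variables and chi-squared to categorical ones, and a 5-point rating could be placed under either.
4. The protocol mixes past and future tense, so it is unclear whether patients have already been enrolled. If enrolment has begun and the item cannot be collected from all patients, do not report it from a subset as the titled outcome. Restate the titled outcome and the conclusion as quality of recovery.

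The cost is one question at a contact that already takes place, plus wording changes. No visit or procedure is added. The downside is that a single item is coarser than a 40-item score and may show ties or a ceiling. If only the wording changes, the trial makes a narrower claim.

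### The blanket test rule exempts no pre-procedure variable: about 21 baseline characteristics would be significance-tested between randomised groups, which yields about one chance finding and cannot show comparability

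*Combined protocol and SAP*

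**What the plan says.** The Statistical Analysis section of the combined protocol and SAP gives its reason for the choice of method in one sentence: "As some pre and anesthetic characteristics of patients will be distributed abnormally nonparametric statistics will be used". Two unrestricted rules follow. For continuous data: "Continuous variables will be compared between the groups using Mann-Whitney U-test". Categorical data are to be "compared between the groups using Chi-Squared Test". The significance level is 0.05. Sidedness and multiplicity are not addressed.

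The variables are listed in the Study Protocol section, in one sequence that mixes characteristics present before treatment with quantities that arise during it: "Age, gender, height, weight, body mass index (BMI), ASA scores, laboratory values, duration of anesthesia" and so on, through procedure time and drug doses to infertility history and complications. Vital signs are recorded before, during and after the procedure. STAI TX-1 is completed once, 2 hours before the procedure. QoR-40 is completed 24 hours after discharge.

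On allocation, the paragraph before the Statistical Analysis heading says that "140 patients will be randomly allocated to two study groups", with 70 in each. Nothing limits pre-procedure data to description. No baseline covariate and no adjusted analysis is named.

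**The concern.** A between-group test on a variable fixed before randomisation asks whether chance produced the difference. If allocation was sound, the answer is already known to be yes. A small p-value then carries no information about the treatments, and a large one does not show that an imbalance is unimportant for the outcome. Importance depends on the size of the imbalance and on how strongly the variable predicts the outcome, and the test measures neither.

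Two things are at stake. A chance p<0.05 can cast doubt on a sound randomisation or invite adjustment chosen after the data are seen. A column of non-significant p-values can be read as evidence of balance, leaving a prognostic variable unadjusted. The plan offers no alternative safeguard, because it prespecifies no covariate and neither of its tests can take one.

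**Working it through.** The plan gives no figure of its own on this point (no effect size, SD or power statement), so there is nothing to reproduce beyond 70 + 70 = 140.

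**Inputs from the documents.** 70 per arm; 0.05 per test (two-sided assumed); the variable list in the Study Protocol section. Gender is left out because all patients are female.

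**Count of testable pre-procedure variables**, each listed item taken as one variable:

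| Group | Number |
|---|---|
| Age, height, weight, BMI, ASA class | 5 |
| Laboratory values | 6 |
| Comorbidity; symptoms before the procedure | 2 |
| Infertility: cause; duration | 2 |
| Vital signs at the preoperative time point | 6 |
| **Total without STAI TX-1** | **21** (17 continuous, 4 categorical) |
| **Total with STAI TX-1** | **22** |

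**Expected number of p<0.05 under sound randomisation** = k × 0.05. This does not require independence.
- k = 21: 21 × 0.05 = 1.05
- k = 22: 22 × 0.05 = 1.10

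**Chance of at least one** = 1 − 0.95^k. This does depend on independence.
- Independent, k = 21: 1 − 0.95^21 = 65.9%
- Independent, k = 22: 1 − 0.95^22 = 67.6%
- Correlated, with 10 effective tests (assumed): 1 − 0.95^10 = 40.1%

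Hemoglobin with hematocrit, weight with BMI, and the three blood pressures are plainly correlated, so the independent figures are at the upper end.

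**Smallest continuous imbalance that reaches p<0.05**, in SD units:
- Normal approximation: 1.96 × √(2/70) = 0.331
- t quantile: 0.334
- Mann-Whitney, normal data: 0.331 / √(3/π) = 0.339

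In a simulation of 40,000 Mann-Whitney tests on normal data at 70 v 70, the type I error was 4.8%. The mean absolute difference at p close to 0.05 was 0.32 SD, and 99% of non-significant results lay below 0.34 SD. For categorical variables the threshold is only approximate.

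**What an unflagged imbalance could do.** The shift in the outcome contrast is r × imbalance, where r is the baseline–outcome correlation. The documents give no r; 0.3 to 0.5 is assumed. The effect detectable with 80% power at 70 per arm is 0.477 SD by t-test, or 0.477 / √0.955 = 0.488 SD by Mann-Whitney.
- Typical case: the standard error of the imbalance is √(2/70) = 0.169 SD, so its mean absolute size is about 0.135 SD. The shift is 0.04–0.07 SD, about 8–14% of 0.488.
- Tail case: an imbalance of 0.30 SD gives a shift of 0.09–0.15 SD, about 18–31% of 0.488. An imbalance of 0.30 SD or more occurs about 7.6% of the time for a given variable. One between 0.30 and 0.33 SD, large yet unflagged, occurs about 2.6% of the time.

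**The case against.** The strongest reply is that the plan never says that it will test baseline characteristics. The sentence about distributions only explains the preference for nonparametric methods, and the sentences after it are generic. This is fair: baseline testing is an inference. It remains the plain reading, because the rule has no exception and the stated reason for it is the distribution of pre-procedure characteristics.

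Several stronger readings are tempting, and the documents do not support them.

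- **A reader might infer that the report will probably contain a false baseline difference.** That holds only near independence. At 10 effective tests the chance is about 40%, below even odds. An expected count of about one is as far as the arithmetic goes.
- **A reader might infer that the treatment comparison is biased.** It is not, on average. The unadjusted test's 5% error rate already covers chance imbalance.
- **A reader might take 18–31% of the detectable effect as the usual cost.** It is a tail case and rests on an assumed correlation.
- **A reader might say that any baseline p<0.05 can only be chance.** That needs variables fixed before a sound allocation. The plan names the randomisation software but not the timing of allocation or its concealment, so symptoms or vital signs could be recorded after the group is known.
- **A reader might say that the plan treats p≥0.05 as proof of balance.** It states no rule for acting on baseline p-values in either direction. That reading is custom, not text.

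A further objection concerns the remedy. Removing all pre-procedure tests also removes the only anxiety comparison that the plan could make, since STAI TX-1 is recorded only before the procedure. Covariate adjustment also cannot be done with the planned tests. Both points stand, and the fix has to deal with them openly.

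**Conclusion.** The point holds as a matter of reporting and prespecification. As written, the plan would test about 21 pre-procedure variables (22 with STAI TX-1) between randomised groups and should expect about one p<0.05 from chance alone. The same tests would generally miss a continuous imbalance below about a third of an SD. They therefore cannot establish comparability and should not decide what is adjusted for.

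The conclusion rests on reading the test rule as applying to all listed variables, on sound allocation, and on two-sided tests that hold their 5% level; sparse chi-squared tables may depart from it. The point should be corrected, but it does not invalidate the randomised comparison.

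**What to change.** 1. Tabulate all pre-procedure variables by randomised group, without p-values.
2. Restrict between-group tests to variables measured after anesthesia starts.
3. Report anesthesia time, procedure time and drug doses as post-randomisation results. The assigned technique can influence them, so they should be neither baseline characteristics nor covariates.
4. Prespecify an outcome model, for example ANCOVA or rank-based ANCOVA for QoR-40. It should adjust for a few variables already collected, such as pre-procedure STAI TX-1 and age, whatever their observed balance. Choose them on prognostic grounds, and confirm that they are recorded before the allocation is known.
5. State explicitly that STAI TX-1, taken only 2 hours before the procedure, is a baseline covariate and cannot serve as a between-group anxiety outcome.

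The cost is one model beyond the planned tests and the loss of the customary baseline p-value column. No new data or patients are needed. Item 5 also makes plain that the current schedule contains no post-procedure anxiety measurement by this scale, although anxiety is in the title.
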